#### 6.4.4.4 Analysis of neutralization magnitude-breadth curves

The area-under-the-magnitude-breadth curve (AUC-MB) to the panel of isolates will be computed for each participant with evaluable neutralization data, as described in Huang et al. (52). Methods for comparing AUC-MB are similar to those described in Section 6.4.4.3.

#### 6.4.4.5 Analysis of CD4+ and CD8+ T-cell response as measured by the ICS assay

The analysis of CD4+ and CD8+ T-cell response rates as measured by the ICS assay will be evaluated and compared as described under the general approach. For each T-cell subset, the positivity call for each peptide pool will include a multiple comparison adjustment for the number of peptide pools used in the

assay. In general, the Mixture Models for Single-cell Assays (MIMOSA) statistical framework (53) and/or the Fisher's exact test-based positivity criteria will be used. Details of the positivity criteria will be discussed in the SAP. The magnitude of marginal response will be analyzed as described for quantitative data in the general approach section. For each T-cell subset, graphs will be used to display the background-subtracted magnitudes for each participant by protein, treatment arm and timepoint. When 3 or more cytokines are being measured by the ICS assay, the polyfunctionality of ICS responses may also be analyzed as an exploratory endpoint. Besides descriptive plots of the magnitude of polyfunctional responses, the COMPASS (Combinatorial Polyfunctionality analysis of Antigen-Specific T-cell Subsets) statistical framework (54) may also be used to perform joint modelling of multiple T-cell subsets of different cytokine combinations. For example, the functionality score (FS) and the polyfunctionality score (PFS) may be used to summarize the multi-parameter ICS responses.

#### **6.4.5 Analyses and data sharing prior to end of scheduled follow-up visits**

Any analyses conducted prior to the end of the scheduled follow-up visits should not compromise the integrity of the trial in terms of participant retention or safety or immunogenicity endpoint assessments. In particular, early unblinded analyses by treatment assignment require careful consideration and should be made available on a need to know basis in accordance with Section 6.4.5.1. Interim blinded safety and immunogenicity data should not be shared outside of the SMB, HVTN 123 PSRT, the protocol team leadership, the HVTN Executive Management Team, the study product developer, and the study sponsor and/or its designee(s) for their regulatory reporting unless approved by the protocol leadership and the HVTN leadership.

##### **6.4.5.1 Safety analyses**

During the course of the trial, unblinded analyses of safety data will be prepared approximately every 4 months for review by the SMB. Ad hoc safety reports may also be prepared for SMB review at the request of the HVTN 123 PSRT. Refer to the process described in the HVTN Unblinding MOP for any requests for unblinded safety data prior to the end of the scheduled follow-up visits.

## 7 Selection and withdrawal of participants

Participants will be healthy, HIV uninfected (seronegative) adults who comprehend the purpose of the study and have provided written informed consent. Volunteers will be recruited and screened; those determined to be eligible, based on the inclusion and exclusion criteria, will be enrolled in the study. Final eligibility determination will depend on information available at the time of enrollment, including results of screening laboratory tests, medical history, physical examinations, and answers to self-administered and/or interview questions.

Investigators should always use good clinical judgment in considering a volunteer's overall fitness for trial participation. Some volunteers may not be appropriate for enrollment even if they meet all inclusion/exclusion criteria. Medical, psychiatric, occupational, or other conditions may make evaluation of safety and/or immunogenicity difficult, and some volunteers may be poor candidates for retention.

Determination of eligibility, taking into account all inclusion and exclusion criteria, must be made within 56 days prior to enrollment unless otherwise noted in Sections [7.1](#) and [7.2](#).

### 7.1 Inclusion criteria

#### General and Demographic Criteria

1. **Age** of 18 to 50 years
2. **Access to a participating HVTN CRS** and willingness to be followed for the planned duration of the study
3. Ability and willingness to provide **informed consent**
4. **Assessment of understanding**: volunteer demonstrates understanding of this study; completes a questionnaire prior to first vaccination with verbal demonstration of understanding of all questionnaire items answered incorrectly
5. **Willing to be contacted in person or by phone**, text message, or e-mail 6 months after completion of the scheduled clinic visits
6. **Agrees not to enroll in another study** of an investigational research agent before the last required protocol clinic visit
7. **Good general health** as shown by medical history, physical exam, and screening laboratory tests

## **HIV-Related Criteria**

8. Willingness to receive **HIV test results**
9. Willingness to discuss HIV infection risks and amenable to HIV risk reduction counseling
10. Assessed by the clinic staff as being at “**low risk**” for **HIV infection** and committed to maintaining behavior consistent with low risk of HIV exposure through the last required protocol clinic visit. (see [Appendix I](#)).

## **Laboratory Inclusion Values**

### **Hemogram/Complete blood count (CBC)**

11. **Hemoglobin**  $\geq$  11.0 g/dL for volunteers who were assigned female sex at birth,  $\geq$  13.0 g/dL for volunteers who were assigned male sex at birth. For transgender participants who have been on hormone therapy for more than 6 consecutive months, determine hemoglobin eligibility based on the gender with which they identify (ie, a transgender female who has been on hormone therapy for more than 6 consecutive months should be assessed for eligibility using the hemoglobin parameters for persons assigned female sex at birth).
12. **White blood cell count** = 3,300 to 12,000 cells/mm^3
13. **Total lymphocyte count**  $\geq$  800 cells/mm^3
14. **Remaining differential** either within institutional normal range or with site physician approval
15. **Platelets** = 125,000 to 550,000/mm^3

### **Chemistry**

16. **Chemistry panel: alanine aminotransferase (ALT), aspartate aminotransferase (AST), and alkaline phosphatase**  $<$  1.25 times the institutional upper limit of normal; **creatinine**  $\leq$  institutional upper limit of normal.

### **Virology**

17. **Negative HIV-1 and -2 blood test:** US volunteers must have a negative FDA-approved enzyme immunoassay (EIA).
18. **Negative Hepatitis B surface antigen (HBsAg)**
19. **Negative anti-Hepatitis C virus antibodies (anti-HCV)**, or negative HCV polymerase chain reaction (PCR) if the anti-HCV is positive

## **Urine**

### **20. Normal urine:**

- Negative urine glucose, and
- Negative or trace urine protein, and
- Negative or trace urine hemoglobin (if trace hemoglobin is present on dipstick, a microscopic urinalysis with red blood cells levels within institutional normal range).

## **Reproductive Status**

**21. Volunteers who were assigned female sex at birth:** negative serum or urine beta human chorionic gonadotropin ( $\beta$ -HCG) pregnancy test performed prior to vaccination on the day of initial vaccination. Persons who are NOT of reproductive potential due to having undergone total hysterectomy or bilateral oophorectomy (verified by medical records), are not required to undergo pregnancy testing.

**22. Reproductive status:** A volunteer who was assigned female sex at birth must:

- Agree to use effective contraception for sexual activity that could lead to pregnancy from at least 21 days prior to enrollment until 3 months after the final study vaccination. Effective contraception is defined as using the following methods:
  - Condoms (male or female) with or without a spermicide,
  - Diaphragm or cervical cap with spermicide,
  - Intrauterine device (IUD),
  - Hormonal contraception, or
  - Any other contraceptive method approved by the HVTN 123 PSRT
  - Successful vasectomy in any partner assigned male sex at birth (considered successful if a volunteer reports that a male partner has [1] documentation of azoospermia by microscopy, or [2] a vasectomy more than 2 years ago with no resultant pregnancy despite sexual activity postvasectomy);
- Or not be of reproductive potential, such as having reached menopause (no menses for 1 year) or having undergone hysterectomy, bilateral oophorectomy, or tubal ligation;
- Or be sexually abstinent.

23. **Volunteers who were assigned female sex at birth must also agree not to seek pregnancy through alternative methods**, such as artificial insemination or in vitro fertilization until after the last required protocol clinic visit

## 7.2 Exclusion criteria

### General

1. **Blood products** received within 120 days before first vaccination
2. **Investigational research agents** received within 30 days before first vaccination
3. **Body mass index (BMI)  $\geq 40$** ; or  $\text{BMI} \geq 35$  with 2 or more of the following: age  $> 45$ , systolic blood pressure  $> 140$  mm Hg, diastolic blood pressure  $> 90$  mm Hg, current smoker, known hyperlipidemia
4. **Intent to participate in another study** of an investigational research agent or any other study that requires non-HVTN HIV antibody testing during the planned duration of the HVTN 123 study
5. **Pregnant or breastfeeding**
6. **Active duty and reserve US military personnel**

### Vaccines and other Injections

7. **HIV vaccine(s)** received in a prior HIV vaccine trial. For volunteers who have received control/placebo in an HIV vaccine trial, the HVTN 123 PSRT will determine eligibility on a case-by-case basis.
8. **Previous receipt of monoclonal antibodies (mAbs)**, whether licensed or investigational; the HVTN 123 PSRT will determine eligibility on a case-by-case basis.
9. **Non-HIV experimental vaccine(s) received within the last 5 years** in a prior vaccine trial. Exceptions may be made by the HVTN 123 PSRT for vaccines that have subsequently undergone licensure by the FDA. For volunteers who have received control/placebo in an experimental vaccine trial, the HVTN 123 PSRT will determine eligibility on a case-by-case basis. For volunteers who have received an experimental vaccine(s) greater than 5 years ago, eligibility for enrollment will be determined by the HVTN 123 PSRT on a case-by-case basis.
10. **Live attenuated vaccines** received within 30 days before first vaccination or scheduled within 14 days after injection (eg, measles, mumps, and rubella [MMR]; oral polio vaccine [OPV]; varicella; yellow fever)

11. **Any vaccines that are not live attenuated vaccines** and were received within 14 days prior to first vaccination (eg, tetanus, pneumococcal, Hepatitis A or B)
12. **Allergy treatment with antigen injections** within 30 days before first vaccination or that are scheduled within 14 days after first vaccination

### **Immune System**

13. **Immunosuppressive medications** received within 168 days before first vaccination (Not exclusionary: [1] corticosteroid nasal spray; [2] inhaled corticosteroids; [3] topical corticosteroids for mild, uncomplicated dermatitis; or [4] a single course of oral/parenteral prednisone or equivalent at doses  $\leq$  60 mg/day and length of therapy  $<$  11 days with completion at least 30 days prior to enrollment)
14. **Serious adverse reactions to vaccines** including history of anaphylaxis and related symptoms such as hives, respiratory difficulty, angioedema, and/or abdominal pain. (Not excluded from participation: a volunteer who had a nonanaphylactic adverse reaction to pertussis vaccine as a child.)
15. **Immunoglobulin** received within 60 days before first vaccination
16. **Autoimmune disease**
17. **Immunodeficiency**

### **Clinically significant medical conditions**

18. **Clinically significant medical condition**, physical examination findings, clinically significant abnormal laboratory results, or past medical history with clinically significant implications for current health. A clinically significant condition or process includes but is not limited to:
  - A process that would affect the immune response,
  - A process that would require medication that affects the immune response,
  - Any contraindication to repeated injections or blood draws,
  - A condition that requires active medical intervention or monitoring to avert grave danger to the volunteer's health or well-being during the study period,
  - A condition or process for which signs or symptoms could be confused with reactions to vaccine, or
  - Any condition specifically listed among the exclusion criteria below.

19. **Any medical, psychiatric, occupational, or other condition** that, in the judgment of the investigator, would interfere with, or serve as a contraindication to, protocol adherence, assessment of safety or reactogenicity, or a volunteer's ability to give informed consent
20. **Psychiatric condition that precludes compliance with the protocol.**  
Specifically excluded are persons with psychoses within the past 3 years, ongoing risk for suicide, or history of suicide attempt or gesture within the past 3 years.
21. **Current anti-tuberculosis (TB) prophylaxis or therapy**
22. **Asthma exclusion criteria:**

**Asthma** other than mild, well-controlled asthma. (Symptoms of asthma severity as defined in the most recent National Asthma Education and Prevention Program (NAEPP) Expert Panel report).

Exclude a volunteer who:

  - Uses a short-acting rescue inhaler (typically a beta 2 agonist) daily, or
  - Uses moderate/high dose inhaled corticosteroids, or
  - In the past year has either of the following:
    - Greater than 1 exacerbation of symptoms treated with oral/parenteral corticosteroids;
    - Needed emergency care, urgent care, hospitalization, or intubation for asthma.
23. **Diabetes mellitus** type 1 or type 2 (Not excluded: type 2 cases controlled with diet alone or a history of isolated gestational diabetes.)
24. **Thyroidectomy, or thyroid disease** requiring medication during the last 12 months
25. **Hypertension:**
  - If a person has been found to have elevated blood pressure or hypertension during screening or previously, exclude for blood pressure that is not well controlled. Well-controlled blood pressure is defined as consistently  $\leq 140$  mm Hg systolic and  $\leq 90$  mm Hg diastolic, with or without medication, with only isolated, brief instances of higher readings, which must be  $\leq 150$  mm Hg systolic and  $\leq 100$  mm Hg diastolic. For these volunteers, blood pressure must be  $\leq 140$  mm Hg systolic and  $\leq 90$  mm Hg diastolic at enrollment.
  - If a person has NOT been found to have elevated blood pressure or hypertension during screening or previously, exclude for systolic blood

pressure  $\geq$  150 mm Hg at enrollment or diastolic blood pressure  $\geq$  100 mm Hg at enrollment.

26. **Bleeding disorder** diagnosed by a doctor (eg, factor deficiency, coagulopathy, or platelet disorder requiring special precautions)
27. **Malignancy** (Not excluded from participation: Volunteer who has had malignancy excised surgically and who, in the investigator's estimation, has a reasonable assurance of sustained cure, or who is unlikely to experience recurrence of malignancy during the period of the study)
28. **Seizure disorder:** History of seizure(s) within past three years. Also exclude if volunteer has used medications in order to prevent or treat seizure(s) at any time within the past 3 years.
29. **Asplenia:** any condition resulting in the absence of a functional spleen
30. History of hereditary **angioedema**, acquired angioedema, or idiopathic angioedema.

### **7.3 Participant departure from vaccination schedule or withdrawal**

This section concerns an individual participant's departure from the study product administration schedule. Pause rules for the trial are described in Section [11.3](#).

#### **7.3.1 Delaying vaccinations for a participant**

Under certain circumstances, a participant's scheduled vaccination will be delayed. The factors to be considered in such a decision include but are not limited to the following:

- Within 45 days prior to any study injection
  - Receipt of blood products or immunoglobulin
- Within 30 days prior to any study injection
  - Receipt of live attenuated vaccines
  - Receipt of allergy treatment with antigen injections
- Within 14 days prior to any study injection
  - Receipt of any vaccines that are not live attenuated vaccines (eg, pneumococcal)
- Prevaccination abnormal vital signs or clinical symptoms that may mask assessment of vaccine reaction.

Vaccinations should not be administered outside the visit window period specified in the HVTN 123 Study Specific Procedures.

In order to avoid vaccination delays and missed vaccinations, participants who plan to receive licensed vaccines or allergy treatments should be counseled to schedule receipt of these substances, when possible, outside the intervals indicated above. The effects of these substances on safety and immunogenicity assessments and their interactions with study vaccines are unknown. Therefore, if circumstances allow, these substances should also be avoided in the 2 week interval between a study vaccination and completion of the 2 week postvaccination follow-up visit.

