##### **6.4.3.1 Reactogenicity**

The number and percentage of participants experiencing each type of reactogenicity sign or symptom will be tabulated by severity and treatment arm and the percentages displayed graphically by arm. For a given sign or symptom, each participant's reactogenicity will be counted once under the maximum severity for all injection visits. In addition, to the individual types of events, the maximum severity of local pain or tenderness, induration or erythema, and of systemic symptoms will be calculated. Wilcoxon tests will be used to test for differences in severity between arms.

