## **9.3 Enrollment and vaccination visits**

Enrollment is simultaneous with first vaccination. The HVTN CRS requests the randomization assignment via a Web-based randomization system. In general, the time interval between randomization and enrollment should not exceed 4 working days. However, circumstances may require a participant's enrollment visit to be changed. This may exceed the 4-day randomization time limit.

At all vaccination visits, the following procedures are performed before vaccination:

- Abbreviated physical examination, including weight, vital signs, and a symptom-directed evaluation by history and/or appropriate physical exam based on participant self-reported symptoms or complaints;

- Assessment of baseline reactogenicity parameters;
- Assessment of concomitant medications (as described in Section [9.2](#));
- Assessment of any new or unresolved AEs/intercurrent illnesses; and
- Urine or serum pregnancy test (for participants who were assigned female sex at birth). Persons who are NOT of reproductive potential due to having undergone total hysterectomy or bilateral oophorectomy (verified by medical records), are not required to undergo pregnancy testing.

Following completion of all procedures in the preceding list, and if results indicate that vaccination may proceed, vaccination is prepared and administered (see Sections [8.3](#) and [8.4](#)).

Immediately following vaccination, the participant remains in the clinic for observation. An initial reactogenicity assessment is made at a target of 30 minutes after injection, with an acceptable range of 25-60 minutes. Before leaving the clinic, the participant is given the Participant Diary and is instructed on how to complete it. The site will make arrangements to be in contact with the participant during the reactogenicity period (as described in Section [9.9](#)).

The following procedures will be performed at all vaccination visits. These procedures may be performed prior to or following vaccination:

- Risk reduction counseling (as described in Section [9.6](#));
- Pregnancy prevention assessment (as described in Section [9.2](#) and [9.7](#)); and
- Assessment of new or unresolved social impacts (site staff will ask participant about the status of any unresolved social impacts and if s/he has experienced any new social impacts as a result of the trial participation).

Additional procedures will be performed at scheduled visits as specified in [Appendix E](#) and [Appendix F](#):

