## 9.9 Assessments of reactogenicity

For all participants, baseline assessments are performed before and reactogenicity assessments are performed after each vaccination. All reactogenicity symptoms are followed until resolution and graded according to the Division of AIDS (DAIDS) Table for Grading the Severity of Adult and Pediatric Adverse Events, Corrected Version 2.1, July 2017, except as noted in Section 11.2.2.

The reactogenicity assessment period is 7 full days following each vaccination per the assessment schedule shown in [Table 9-1](#). Participants are instructed to record symptoms using a Participant Diary. Contacts between the participant and the site

staff should take place at least once between 1-3 days postvaccination. In general, a participant who self-reports any postvaccination reaction greater than mild is seen by a clinician within 48 hours after onset, unless the reaction is improving and/or has completely resolved. Clinic staff will follow new or unresolved reactogenicity symptoms present at day 7 to resolution.

Reactogenicity events are reported using CRFs that correspond to the time of assessment in [Table 9-1](#). Reactogenicity assessments include assessments of systemic and local symptoms, and vaccine-related lesions. Events not listed on a CRF, or with an onset after the reactogenicity assessment period (day of vaccination and 7 full days after), or those meeting SAE/AEs requiring expedited reporting to DAIDS criteria, are recorded on an adverse experience log form.

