**Table 9-1 Schedule of reactogenicity assessments**

Day	Time	Performed by
0 a	Baseline: before vaccination	HVTN CRS clinician
	Early: 25-60 minutes after vaccination	HVTN CRS clinician
	Between early assessment and 11:59pm day 0	HVTN CRS clinician or participant
1-7 b	Between 12:00am and 11:59pm on the respective day	HVTN CRS clinician or participant

a Day of vaccination

b New or unresolved reactogenicity symptoms present on day 7 are followed until resolution

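### The reactogenicity analysis in 6.4.3.1 takes each participant's maximum post-injection severity and makes no use of the baseline assessed before every injection, so an unchanged pre-existing systemic symptom is counted as reactogenicity

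*Protocol*

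**What the plan says.** **Delay rule.** Protocol 7.3.1 names "Prevaccination abnormal vital signs or clinical symptoms that may mask assessment of vaccine reaction" as a ground for delaying an injection. It is a matter for judgement: "The factors to be considered in such a decision include but are not limited to the following". No severity threshold is given, so a participant with a mild symptom may still be injected.

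**Data collection.** Section 9.3 requires "Assessment of baseline reactogenicity parameters" at all vaccination visits. Section 9.9 states that "baseline assessments are performed before and reactogenicity assessments are performed after each vaccination", and Table 9-1 gives the row "Baseline: before vaccination" to the site clinician. Section 9.9 also says "The reactogenicity assessment period is 7 full days following each vaccination". Section 9.9.1 reports the daily maximum severity of each symptom in that period. It has no attribution step and does not refer back to baseline.

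**Analysis.** Under 6.4.3.1, for a given sign or symptom, "each participant's reactogenicity will be counted once under the maximum severity for all injection visits". Arms are compared by Wilcoxon tests on severity. Baseline is not mentioned.

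**SAP.** The supplied SAP (v1.0) covers immunogenicity only and contains no reactogenicity analysis.

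**The concern.** The protocol recognises that existing symptoms can be confused with a reaction and requires a pre-injection assessment at every vaccination visit. It then leaves that assessment out of the analysis.

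Reactogenicity is part of primary endpoint 1. The Wilcoxon tests in 6.4.3.1 are the only between-arm safety tests that the protocol specifies, since 6.4.3.2 plans none for adverse events. Both arms receive active product, so no placebo group shows how much headache or fatigue would have been reported anyway. Two things are at stake: the systemic reactogenicity rates reported for each product, one of them first-in-human, and the sensitivity of the comparison between products.

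**Working it through.** **1. Following the rule through.** Suppose a participant has a grade 1 headache at the pre-injection assessment, is injected, and still has a grade 1 headache on day 1.
- Under 9.9.1, the day 1 value is reported as grade 1.
- Under 6.4.3.1, the maximum over injection visits is at least grade 1.
- The participant is tabulated with headache, and this value enters the Wilcoxon test. No stated step removes it.

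**2. How many participants could be affected.** The documents give no pre-injection prevalence, so *b*, the chance that a given systemic symptom is present before any one injection, is an assumption. With three injections, treated as independent, P(present before at least one) = 1 − (1 − *b*)³. Each arm has 15 participants.

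| *b* | 1 − (1 − *b*)³ | Expected of 15 |
|---|---|---|
| 3% | 8.7% | 1.3 |
| 5% | 14.3% | 2.1 |
| 10% | 27.1% | 4.1 |

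**3. Effect on a per-arm rate.** Let *t* be the vaccine-caused rate over three injections and *q* the share of pre-existing symptoms that persist after injection. Then the recorded rate = 1 − (1 − *t*)(1 − *bq*)³. With *t* = 25% (assumed):
- *b* = 3%: 1 − 0.75 × 0.985³ = 28.3% (*q* = 50%); 1 − 0.75 × 0.97³ = 31.5% (*q* = 100%)
- *b* = 5%: 1 − 0.75 × 0.975³ = 30.5%; 1 − 0.75 × 0.95³ = 35.7%
- *b* = 10%: 1 − 0.75 × 0.95³ = 35.7%; 1 − 0.75 × 0.90³ = 45.3%

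**4. Effect on the Wilcoxon test.** This was simulated with 3,000 trials, 15 per arm and a two-sided asymptotic test at 0.05. Assumed inputs were true rates of 25% and 65%, vaccine-caused grades 1/2/3 at 65/30/5%, and pre-existing grades 1/2 at 85/15%. Each range runs from *q* = 50% to *q* = 100%.

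| *b* | Power, raw maximum | Power, new or worsened only |
|---|---|---|
| 3% | 0.54 to 0.51 | 0.57 to 0.58 |
| 5% | 0.53 to 0.48 | 0.58 to 0.57 |
| 10% | 0.48 to 0.40 | 0.56 to 0.55 |

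With no background symptoms, power is about 0.58 to 0.59. Repeat runs agreed within simulation error: 0.39 to 0.55 raw and 0.55 to 0.60 new-or-worsened. The new-or-worsened count records the true 25% as 23% to 25%.

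**5. Type I error.** In a separate simulation (4,000 runs per setting, equal background in both arms, *b* from 0 to 15%), the raw-maximum test rejected in 4.4% to 4.8% of null trials.

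**6. A smaller difference.** At 25% against 45%, power is about 0.19 with no background symptoms at all. At *b* of 3% to 5% it is 0.15 to 0.17 raw and 0.18 to 0.19 new-or-worsened.

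**The case against.** **Silence is not a stated rule.** No section says that pre-existing symptoms are to be counted. Section 6.4 defers one safety question to the SAP, and the supplied SAP is for immunogenicity, so a safety rule may exist elsewhere. This limits the point to what the protocol says. It does not remove it, because 6.4.3.1 applied to the values reported under 9.9.1 gives the result in step 1.

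**The protocol already limits the problem.** Exclusion 18 keeps out volunteers with a condition whose signs or symptoms could be taken for vaccine reactions. Section 9.3 has new or unresolved illness assessed before each injection, and 7.3.1 allows a delay. These stand as mitigations, and the calculation models none of them. A reader might take the delay rule as the error or as contradicting 6.4.3.1. It is neither: the gap lies in the analysis section.

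**The pre-injection value itself.** Because Table 9-1 lists baseline among the reactogenicity assessments, a reader might infer that the baseline value enters the maximum. Section 9.9 does not support this. It places reactogenicity assessments after vaccination and starts the assessment period there, and 9.9.1 confines the reported maximum to that period.

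**Baseline grading.** A reader might also assume that every symptom is graded at baseline. The text says that baseline parameters are assessed; the grading rule, "All reactogenicity symptoms are followed until resolution and graded according to", is stated for reactogenicity symptoms. The case report form is not among the documents.

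**Caution.** For a first-in-human product, over-counting is the conservative direction. That is a good reason to keep the raw maximum as a main display.

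**Conclusion.** The point holds as an omission in 6.4.3.1. The stated rule counts unchanged pre-existing systemic symptoms as reactogenicity, and the supplied documents contain nothing that corrects this.

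The effect is inflation of per-arm systemic rates and some dilution of the between-arm contrast. Under assumed prevalences of 3% to 10% per visit, a true 25% is recorded as about 28% to 45%. Power for a 25% against 65% difference falls from about 0.58 to between 0.54 and 0.40. The loss is small at low prevalence. Prevalence, persistence, independence across visits, grade mix and true rates are all assumed, so the actual size is unknown.

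The documents do not support a reading in which the analysis favours one product or produces false positives. Assignment is randomised and blinded, background symptoms should be similar in the two arms on average, and type I error stays below 5%. Chance imbalance remains possible at 15 per arm. Local reactions are hardly affected, because injections are at least 56 days apart (days 0, 56 and 168). Nor would the change make the test informative for modest differences: at 25% against 45%, power stays below 0.20 either way.

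**What to change.** In 6.4.3.1:
1. State that the maximum uses post-injection assessments only, from after the injection on day 0 through day 7.
2. Keep the raw-maximum tabulation and its Wilcoxon tests.
3. Pre-specify beside them a new-or-worsened tabulation and Wilcoxon test for systemic symptoms. A symptom counts at an injection only if its highest post-injection grade exceeds the baseline recorded before that same injection. Each participant's value is the maximum of the counted grades over injections.
4. Confirm that the baseline record uses the same severity scale as the post-injection assessments, since the comparison depends on it.

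**Cost.** A few sentences and minor programming. The baseline assessment is already required at every injection, so no visits are added. The downside is that a true reaction no worse than the pre-existing symptom is missed in the new-or-worsened analysis; in the simulation this took a true 25% to 23% to 25%. Such a reaction remains visible in the raw table. The delay rule in 7.3.1 and all other clinical rules stay as they are.
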